4.5.9 Optional Long-Term Follow-Up

Patients enrolled in the study will be asked to participate in optional long-term follow-up, which will include collection of long-term survival data beyond the end of the study. This long-term data collection will be managed by the Sponsor's designee. The patient may withdraw consent from optional long-term follow-up at any time during or after the study by e-mail.

Long-term follow-up will be initiated after the study end or if the study is terminated for any reason. *Survival data will be collected during the optional long-term follow-up period every 3 months for the first year, then every 6 months thereafter for up to 5 years from enrollment of the first patient into the study, until the last patient dies, withdraws consent, or is lost to follow-up, whichever occurs first.*

4.5.10 ECOG Performance Status

ECOG performance status (see [Appendix 6](#)) will be measured at the visits specified in [Appendix 1](#).

4.6 PATIENT, TREATMENT, STUDY, AND SITE DISCONTINUATION

4.6.1 Patient Discontinuation

Patients have the right to voluntarily withdraw from the study at any time for any reason. In addition, the investigator has the right to withdraw a patient from the study at any time. Reasons for withdrawal from the study may include, but are not limited to, the following:

- Patient withdrawal of consent at any time
- Any medical condition that the investigator or Sponsor determines may jeopardize the patient's safety if he or she continues in the study
- Investigator or Sponsor determines that it is in the best interest of the patient
- Patient non-compliance
- Patient is lost to follow-up

Every effort should be made to obtain information on patients who withdraw from the study. The primary reason for withdrawal from the study should be documented on the appropriate eCRF. However, patients will not be followed for any reason after consent has been withdrawn. Patients who withdraw from the study will not be replaced.

4.6.2 Study Treatment Discontinuation

Patients must discontinue study drug if they experience any of the following (but will remain in the study and be evaluated for safety and efficacy):

- Pregnancy
- Intolerable toxicity related to study drug
- Any medical condition that may jeopardize the patient's safety if he or she continues with study drug
- Use of another systemic anti-cancer therapy (see Section 4.1.2)
- Radiographic disease progression per RECIST v1.1
 - **Exception:** Patients will be permitted to continue atezolizumab after RECIST v1.1 criteria for PD are met if they meet all of the following criteria:
 - Evidence of clinical benefit (defined as the stabilization or improvement of disease-related symptoms) as assessed by the investigator
 - Absence of symptoms and signs (including worsening of laboratory values [e.g., new or worsening hypercalcemia]) indicating unequivocal progression of disease
 - No decline in ECOG Performance Status that can be attributed to disease progression
 - Absence of tumor progression at critical anatomical sites (e.g., leptomeningeal disease) that cannot be readily managed and stabilized by protocol-allowed medical interventions prior to repeat dosing

When a patient discontinues study drug, regardless of the reason for discontinuation, the patient will be asked to return to the clinic within 30 days after the last dose of study drug for a study drug discontinuation visit. The visit at which the decision is made to discontinue treatment (e.g., loss of clinical benefit is confirmed or disease progression occurs) may be used as the study-drug discontinuation visit. The primary reason for study drug discontinuation should be documented on the appropriate eCRF. Patients who discontinue study drug prematurely will not be replaced.

4.6.3 Study and Site Discontinuation

The Sponsor has the right to terminate this study at any time. Reasons for terminating the study may include, but are not limited to, the following:

- The incidence or severity of adverse events in this or other studies indicates a potential health hazard to patients.
- Patient enrollment is unsatisfactory.
- The prespecified futility analysis is met (see Section 6.7)

The Sponsor will notify the investigator if the Sponsor decides to discontinue the study.

The Sponsor has the right to close a site at any time. Reasons for closing a site may include, but are not limited to, the following:

- Excessively slow recruitment
- Poor protocol adherence
- Inaccurate or incomplete data recording
- Non-compliance with the International Conference on Harmonisation (ICH) guideline for Good Clinical Practice
- No study activity (i.e., all patients have completed the study and all obligations have been fulfilled)

5. ASSESSMENT OF SAFETY

5.1 SAFETY PLAN

Atezolizumab is approved in the United States for the treatment of locally advanced or metastatic UC. The safety plan for patients in this study is based on clinical experience with atezolizumab in completed and ongoing studies. The anticipated important safety risks are outlined below (see Section 5.1.1).

Measures will be taken to ensure the safety of patients participating in this study, including the use of stringent inclusion and exclusion criteria and close monitoring of patients during the study. Administration of atezolizumab will be performed in a monitored setting in which there is immediate access to trained personnel and adequate equipment and medicine to manage potentially serious reactions. After initiation of study drug, all adverse events will be reported until 30 days after the last dose of study drug or until initiation of new anti-cancer therapy, whichever occurs first, and serious adverse events and adverse events of special interest will continue to be reported until 90 days after the last dose of study drug or until initiation of new anti-cancer therapy, whichever occurs first. Guidelines for managing anticipated adverse events, including criteria for dosage modification and treatment interruption or discontinuation, are provided below (see Section 5.1.2). Refer to Section 5.2, Section 5.3, Section 5.4, Section 5.5, and Section 5.6 for details on safety reporting during the study.

5.1.1 Risks Associated with Atezolizumab

Atezolizumab has been associated with risks such as the following: infusion-related reactions and immune-related hepatitis, pneumonitis, colitis, pancreatitis, diabetes mellitus, hypothyroidism, hyperthyroidism, adrenal insufficiency, hypophysitis, Guillain-Barré syndrome, myasthenic syndrome or myasthenia gravis, meningoencephalitis, and myocarditis.

Refer to the Atezolizumab Investigator's Brochure for a detailed description of anticipated safety risks for atezolizumab.

Systemic immune activation is a rare condition characterized by an excessive immune response. Given the mechanism of action of atezolizumab, systemic immune activation is considered a potential risk when given in combination with other immunomodulating agents. Systemic immune activation should be included in the differential diagnosis for patients who, in the absence of an alternative etiology, develop a sepsis-like syndrome after administration of atezolizumab.

The initial evaluation should include the following:

- CBC with peripheral smear
- PT, PTT, fibrinogen, and D-dimer
- Ferritin
- Triglycerides
- AST, ALT, and total bilirubin
- LDH
- Complete neurologic and abdominal examination (assess for hepatosplenomegaly)

If systemic immune activation is still suspected after the initial evaluation, contact the Medical Monitor for additional recommendations.

5.1.2 Management of Patients Who Experience Specific Adverse Events

There will be no dose modifications for atezolizumab in this study.

Study treatment may be temporarily suspended in patients experiencing toxicity that is considered to be related to study drug. If atezolizumab is withheld for >105 days, the patient will be discontinued from atezolizumab. If the investigator believes the patient is likely to derive clinical benefit and the Medical Monitor is in agreement, atezolizumab treatment can be resumed after being withheld for >105 days. If a patient must be tapered off corticosteroids used to treat adverse events, study drug may be withheld for >105 days. The investigator and the Medical Monitor will determine the acceptable length of treatment interruption.

Dose interruptions for reasons other than toxicity (e.g., surgical procedures) may be allowed with Medical Monitor approval. The investigator and the Medical Monitor will determine the acceptable length of treatment interruption.

Guidelines for management of patients who experience specific adverse events associated with atezolizumab are provided in the Atezolizumab Investigator's Brochure and in [Appendix 8](#).

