Pulmonary event, Grade 2	
 • Withhold atezolizumab for up to 12 weeks after event onset.^a • Refer patient to pulmonary and infectious disease specialists and consider bronchoscopy or BAL. • Initiate treatment with 1–2 mg/kg/day oral prednisone or equivalent. • If event resolves to Grade 1 or better, resume atezolizumab.^b • If event does not resolve to Grade 1 or better while withholding atezolizumab, permanently discontinue atezolizumab and contact Medical Monitor.^c • For recurrent events, treat as a Grade 3 or 4 event.
Pulmonary event, Grade 3 or 4	
 • Permanently discontinue atezolizumab and contact Medical Monitor.^c • Bronchoscopy or BAL is recommended. • Initiate treatment with 1–2 mg/kg/day oral prednisone or equivalent. • If event does not improve within 48 hours after initiating corticosteroids, consider adding an immunosuppressive agent. • If event resolves to Grade 1 or better, taper corticosteroids over ≥ 1 month.

BAL=bronchoscopic alveolar lavage.

^a Atezolizumab may be withheld for a longer period of time (i.e., > 12 weeks after event onset) to allow for corticosteroids (if initiated) to be reduced to ≤ 10 mg/day oral prednisone or equivalent. The acceptable length of the extended period of time must be agreed upon by the investigator and the Medical Monitor.

^b If corticosteroids have been initiated, they must be tapered over ≥ 1 month to ≤ 10 mg/day oral prednisone or equivalent before atezolizumab can be resumed.

^c Resumption of atezolizumab may be considered in patients who are deriving benefit and have fully recovered from the immune-related event. Patients can be re-challenged with atezolizumab only after approval has been documented by both the investigator (or an appropriate delegate) and the Medical Monitor.

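### Section 5.1.2 and twelve Appendix 8 rows set different limits, clocks and restart conditions for holding atezolizumab, and neither is said to govern, so some patients get conflicting instructions

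*Protocol*

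**What the plan says.** **Protocol Section 5.1.2.** The general limit is: "If atezolizumab is withheld for >105 days, the patient will be discontinued from atezolizumab". The section does not define the day from which withholding is counted. Two relaxations follow. The first concerns restarting past the limit: "If the investigator believes the patient is likely to derive clinical benefit and the Medical Monitor is in agreement, atezolizumab treatment can be resumed". The second concerns steroids: "If a patient must be tapered off corticosteroids used to treat adverse events, study drug may be withheld for >105 days", with the length settled by the investigator and the Medical Monitor. The section closes with a pointer: "Guidelines for management of patients who experience specific adverse events associated with atezolizumab are provided in the Atezolizumab" Investigator's Brochure and in Appendix 8. It does not say which text prevails if they differ.

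**Protocol Appendix 8.** Twelve rows carry the instruction "Withhold atezolizumab for up to 12 weeks after event onset":

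- pulmonary, Grade 2
- hepatic, Grade 2 lasting more than 5 days
- diarrhea or colitis, Grade 2 and Grade 3 (two rows)
- symptomatic adrenal insufficiency, Grade 2–4
- hypophysitis, Grade 2–3
- ocular, Grade 2
- myocarditis, Grade 2
- amylase or lipase elevation, Grade 3–4
- pancreatitis, Grade 2–3
- dermatologic, Grade 3
- neuropathy, Grade 2

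In these rows the consequence of non-resolution is: "If event does not resolve to Grade 1 or better while withholding atezolizumab, permanently discontinue atezolizumab and contact Medical Monitor" (the adrenal row adds stability on replacement therapy). Footnote a gives the extension: "Atezolizumab may be withheld for a longer period of time (i.e., > 12 weeks after event onset) to allow for corticosteroids" to be brought down to a low oral dose. Footnote b requires that taper before restart. Footnote c sets the condition for re-challenge after permanent discontinuation: "Resumption of atezolizumab may be considered in patients who are deriving benefit and have fully recovered from the immune-related event", with approval documented by both the investigator (or delegate) and the Medical Monitor.

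**The concern.** A site with a patient on hold needs three answers: how long the hold may last, from which day it is counted, and what must be true before dosing restarts. The two texts answer all three differently. Sites cannot easily settle this for themselves, because Protocol Sections 4.3.2 and 5.1 both send them to Section 5.1.2 for the rules on interruption and discontinuation. Section 5.1.2 then refers to Appendix 8 only as guidelines.

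At stake is consistent handling of comparable patients with immune-related toxicity. One site could stop permanently where another keeps the hold open and later re-doses, each following the protocol. The rule also stays in use for a long time, since treatment may run to 32 cycles and continue into the optional long-term follow-up.

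**Working it through.** **Inputs.** Section 5.1.2 limit: 105 days, start undefined. Appendix 8 limit: 12 weeks from onset. Dosing interval: 21 (±3) days (Protocol Section 4.3.2).

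**Step 1, nominal difference.** 12 × 7 = 84 days, and 105 − 84 = 21 days, one dosing interval. Equivalently, 105 = 5 × 21.

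**Step 2, one time axis.** Let *t* be the days from the last dose to event onset. Counted from the last dose, the Appendix 8 limit falls on day 84 + *t*. The Section 5.1.2 limit depends on an assumed clock start:

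- last dose: day 105, so the gap is 105 − (84 + *t*) = 21 − *t*
- event onset: day 105 + *t*, so the gap is 21
- first missed dose (day 21): day 21 + 105 = 126, so the gap is 42 − *t*

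| *t* (days) | Appendix 8 limit (day) | Gap, last-dose clock | Gap, onset clock | Gap, missed-dose clock |
|---|---|---|---|---|
| 0 | 84 | 21 | 21 | 42 |
| 7 | 91 | 14 | 21 | 35 |
| 14 | 98 | 7 | 21 | 28 |
| 21 | 105 | 0 | 21 | 21 |

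For onset 0–21 days after the last dose, Section 5.1.2 therefore expires 0–21, 21, or 21–42 days after Appendix 8. If the +3-day window puts onset at *t* = 24, the last-dose clock gives −3 days: Section 5.1.2 expires first.

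**Step 3, restart conditions side by side.**

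| | Section 5.1.2, past 105 days | Appendix 8, twelve hold rows |
|---|---|---|
| Restart during the permitted hold | no grade stated | Grade 1 or better, steroids tapered if used |
| Restart after the stop | benefit likely | patient deriving benefit and fully recovered |
| Approval | Medical Monitor agrees | documented by investigator and Medical Monitor |
| Steroid-taper extension | yes | yes |

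**Step 4, a patient who gets two answers.** Take a Grade 2 neuropathy, or a Grade 2 ocular event on topical treatment, with no systemic steroids, so that neither steroid extension applies. At day 84 after onset it is still Grade 2. By day 95 after onset it has improved to Grade 1 but has not fully resolved.

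- Appendix 8: permanent discontinuation was due at day 84. Footnote c is not met, because recovery is incomplete.
- Section 5.1.2, onset or missed-dose clock: at day 95 the limit has not been reached and the hold is still open.
- Section 5.1.2, last-dose clock: the limit falls on day 105 − *t* after onset. That is day 98 for *t* = 7 (still open) and day 91 for *t* = 14 (passed). Once passed, resumption needs only likely benefit and Medical Monitor agreement.

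The conflict over hold length disappears only when the two limits coincide. The conflict over restart remains under every clock.

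**The case against.** The best defence is that Section 5.1.2 is a general outer limit and Appendix 8 is the event-specific rule. A site that stops earlier under an Appendix 8 row does not breach a 105-day ceiling. The figure 105 = 84 + 21 even suggests that the two were meant to agree, as 12 weeks plus one cycle. Neither stop is absolute, since both texts allow a longer hold for a steroid taper and both bring in the Medical Monitor. Protocol Section 4.6.2 separately requires stopping for intolerable toxicity or a condition that endangers the patient.

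Much of this narrows the point. It does not remove it. Section 5.1.2 is itself the section on specific adverse events, and it states no precedence. The 12-weeks-plus-one-cycle reading works only if the 105 days run from the last dose and onset falls at the next due dose, and the protocol says neither. Medical Monitor involvement does not settle the matter, because the Monitor also has two standards to apply.

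The defence does defeat several stronger inferences that a reader might draw:

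- *Appendix 8 stops the drug at 12 weeks.* Only twelve rows carry that limit, and the stop depends on non-resolution. Symptomatic thyroid events and Grade 3–4 hyperglycemia are held with no time limit, and many higher-grade events stop the drug at once.
- *Grade 2 pneumonitis unresolved at week 13 shows the conflict.* That row starts prednisone, so footnote a may extend the hold, and Section 5.1.2 has a parallel exception.
- *The gap amounts to one or two extra doses.* It is elapsed time on an assumed clock. Nothing shows that a dose would be given.
- *The safety tables will be distorted.* SAP Section 4.6.2 summarises events leading to discontinuation or interruption. If these are pooled, a held patient is counted under either text. The SAP does not specify a split that would be affected.

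**Conclusion.** The inconsistency is real but limited. Section 5.1.2 and twelve Appendix 8 rows disagree on hold length, start of the clock and conditions for resuming, with no precedence stated. Patients who have fully recovered and are benefiting can be treated under both. Those whose event is unresolved at 84 days after onset, with no steroid extension, can receive contradictory instructions.

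The nominal difference is 21 days. The ranges of 0–21, 21 and 21–42 days rest on three assumed starts for the 105-day clock, on onset 0–21 days after the last dose, and on a missed dose at exactly day 21. The restart conflict needs none of these assumptions. It does rest on Section 5.1.2 being silent about recovery, which is not the same as an instruction to re-dose an unresolved event. The documents give no basis for estimating how many patients would be affected. No endpoint, sample size, power or alpha changes.

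**What to change.** Reconcile Section 5.1.2 and Appendix 8 so that a single hold limit applies, in one unit and with one stated start of the clock. Give one set of conditions for extending the hold and for resuming, including whether recovery is required, to what grade, and how approval is documented. Alternatively, keep both texts and state explicitly which governs for the twelve rows. In either case, replace the duplicated wording with a cross-reference. Which limit and which conditions stand is for the sponsor's clinical team to decide; this review takes no view.

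The cost is a wording change to Section 5.1.2 and to the Appendix 8 rows and footnotes in the next amendment, and slightly less discretion for sites.

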5.2 SAFETY PARAMETERS AND DEFINITIONS

Safety assessments will consist of monitoring and recording adverse events, including serious adverse events and adverse events of special interest, performing protocol-specified safety laboratory assessments, measuring protocol-specified vital signs, and conducting other protocol-specified tests that are deemed critical to the safety evaluation of the study.

Certain types of events require immediate reporting to the Sponsor, as outlined in Section 5.4.

5.2.1 Adverse Events

According to the ICH guideline for Good Clinical Practice, an adverse event is any untoward medical occurrence in a clinical investigation subject administered a pharmaceutical product, regardless of causal attribution. An adverse event can therefore be any of the following:

- Any unfavorable and unintended sign (including an abnormal laboratory finding), symptom, or disease temporally associated with the use of a medicinal product, whether or not considered related to the medicinal product
- Any new disease or exacerbation of an existing disease (a worsening in the character, frequency, or severity of a known condition), except as described in Section 5.3.5.10
- Recurrence of an intermittent medical condition (e.g., headache) not present at baseline
- Any deterioration in a laboratory value or other clinical test (e.g., ECG, X-ray) that is associated with symptoms or leads to a change in study drug or concomitant therapy or discontinuation from study drug
- Adverse events that are related to a protocol-mandated intervention, including those that occur prior to assignment of study drug (e.g., screening invasive procedures such as biopsies)

5.2.2 Serious Adverse Events (Immediately Reportable to the Sponsor)

A serious adverse event is any adverse event that meets any of the following criteria:

- Is fatal (i.e., the adverse event actually causes or leads to death)
- Is life threatening (i.e., the adverse event, in the view of the investigator, places the patient at immediate risk of death)
 - This does not include any adverse event that, had it occurred in a more severe form or was allowed to continue, might have caused death.
- Requires or prolongs inpatient hospitalization (see Section 5.3.5.11)

- Results in persistent or significant disability/incapacity (i.e., the adverse event results in substantial disruption of the patient's ability to conduct normal life functions)
- Is a congenital anomaly/birth defect in a neonate/infant born to a mother exposed to study drug
- Is a significant medical event in the investigator's judgment (e.g., may jeopardize the patient or may require medical/surgical intervention to prevent one of the outcomes listed above)

The terms "severe" and "serious" are not synonymous. Severity refers to the intensity of an adverse event (e.g., rated as mild, moderate, or severe, or according to the NCI CTCAE; see Section 5.3.3); the event itself may be of relatively minor medical significance (such as severe headache without any further findings).

Severity and seriousness need to be independently assessed for each adverse event recorded on the eCRF.

Serious adverse events are required to be reported by the investigator to the Sponsor immediately (i.e., no more than 24 hours after learning of the event; see Section 5.4.2 for reporting instructions).

5.2.3 Adverse Events of Special Interest (Immediately Reportable to the Sponsor)

Adverse events of special interest are required to be reported by the investigator to the Sponsor immediately (i.e., no more than 24 hours after learning of the event; see Section 5.3.5.4 for reporting instructions). Adverse events of special interest for this study include the following:

- Any of the following confirmed treatment-emergent autoimmune conditions:
 - Pneumonitis
 - Colitis
 - Endocrinopathies: diabetes mellitus, pancreatitis, or adrenal insufficiency or hyperthyroidism
 - Hepatitis
 - Transaminitis: Grade ≥ 2 (AST or ALT $>3 \times$ ULN and bilirubin $>2 \times$ ULN) OR AST or ALT $>10 \times$ ULN
 - Systemic lupus erythematosus
 - Neurologic: Guillain-Barré syndrome, myasthenia gravis, meningoencephalitis
 - Nephritis
- Events suggestive of hypersensitivity, cytokine release, influenza-like illness, systemic inflammatory response system, systemic immune activation, or infusion-reaction syndromes

- Cases of potential drug-induced liver injury that include an elevated ALT or AST in combination with either an elevated bilirubin or clinical jaundice, as defined by Hy's law (see Section 5.3.5.7)
- Suspected transmission of an infectious agent by the study drug, as defined below:
 - Any organism, virus, or infectious particle (e.g., prion protein transmitting transmissible spongiform encephalopathy), pathogenic or non-pathogenic, is considered an infectious agent. A transmission of an infectious agent may be suspected from clinical symptoms or laboratory findings that indicate an infection in a patient exposed to a medicinal product. This term applies only when a contamination of the study drug is suspected.

